9.0 CRITERIA FOR RESPONSE

9.1 Response criteria will be modified from the International Working Group for AML (JCO 2003; 21: 4642-9). Responders are patients who obtain a CR, CRi, or PR, with or without cytogenetic response, hematologic improvements, and morphologic leukemia-free state. Briefly, criteria are as follows:

9.1.1 Complete Remission (CR):

- ◆ **Peripheral blood counts:**
No circulating blasts
Neutrophil count $\geq 1.0 \times 10^9/L$
Platelet count $\geq 100 \times 10^9/L$
- ◆ **Bone marrow aspirate and biopsy:**
 $\leq 5\%$ blasts
No Auer rods
No extramedullary leukemia

9.1.2 Complete remission with incomplete blood count recovery (CRi):

- ◆ **Peripheral blood counts:**
No circulating blasts
Neutrophil count $< 1.0 \times 10^9/L$, or
Platelet count $< 100 \times 10^9/L$
- ◆ **Bone marrow aspirate and biopsy:**
 $\leq 5\%$ blasts
No Auer rods
No extramedullary leukemia

9.1.3 Partial Remission (PR):

- ◆ All CR criteria if abnormal before treatment except:
- ◆ $\geq 50\%$ reduction in bone marrow blast but still $> 5\%$

9.1.4 Morphologic Leukemia-Free State (MLF):

- ◆ Bone marrow: $\leq 5\%$ myeloblasts

9.1.5 Hematologic Improvement (HI): Hematologic response must be described by the number of positively affected cell lines.

- ◆ **Erythroid response (E)** (pretreatment Hgb $< 11 \text{ g/dL}$)
Hgb increase by $\geq 1.5 \text{ g/dL}$
- ◆ **Platelet response (P)** (pretreatment platelets $< 100 \times 10^9/L$)
Absolute increase of $\geq 30 \times 10^9/L$ for patients starting with $> 20 \times 10^9/L$ platelets, or
Increase from $< 20 \times 10^9/L$ to $> 20 \times 10^9/L$ and by at least 100%

- ◆ **Neutrophil response (N)** (pretreatment ANC $<1.0 \times 10^9/L$)
At least 100% increase and an absolute increase $>0.5 \times 10^9/L$
- ◆ **Blast response (B):** at least 50% reduction in blast percentage.

9.1.6 Overall Response: An adequate response, included in the overall response rate (ORR) for this trial will include all of the following obtained within the first 3 months of therapy: CR, CRi, PR, MLF, HI.

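### MLF in section 9.1.4 has no baseline condition and none of the CR/CRi exclusions, so it can add to the ORR patients who still show leukemia or have not changed since entry

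*Combined protocol and SAP*

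**What the plan says.** All the response definitions stand in section 9.1 of the combined protocol and SAP.

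- **CR (9.1.1)** and "Complete remission with incomplete blood count recovery (CRi" (9.1.2) share four conditions: "No circulating blasts", marrow blasts of 5% or less, no Auer rods, and "No extramedullary leukemia". They differ only in blood counts. CR needs neutrophils of at least 1.0 and platelets of at least 100 (× 10⁹/L). CRi takes neutrophils below 1.0 or platelets below 100, with no lower limit.
- **MLF (9.1.4)**, headed "Morphologic Leukemia-Free State (MLF", has a single line: "Bone marrow: $\leq 5\%$ myeloblasts". It does not mention circulating blasts, Auer rods, extramedullary disease or the baseline marrow.
- **PR (9.1.3)** needs a marrow blast reduction of at least 50% with blasts still above 5%. **HI (9.1.5)** includes a blast response of at least 50% reduction and does not say whether this is in marrow or blood.
- **ORR (9.1.6)**: "An adequate response, included in the overall response rate (ORR) for this trial will include all of the following", and the list is CR, CRi, PR, MLF and HI within the first 3 months.

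Section 11 tests the ORR against a 1% null in a two-stage design: 14 patients, then 15 more if there is at least one response, with success at 2 or more responses in 29. Its paragraph on enrollment during the interim analysis lists responders as CR+PR+HI, which leaves out both MLF and CRi.

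**The concern.** The name of the category promises absence of leukemia, but its definition drops every sign of leukemia outside the marrow percentage. Whatever CR and CRi exclude on those grounds can re-enter the ORR through MLF.

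MLF also asks for no change. PR and every HI line are defined against the pretreatment state; MLF is not. Eligibility (4.1.1) sets no minimum marrow blast percentage, and 6.5 provides for isolated CNS involvement. A patient with extramedullary disease and a marrow already at 5% or less could therefore be scored a responder at the day-28 marrow with nothing altered.

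The decision rule makes this matter. One response among 14 opens the second stage and two among 29 declare success, so one patient classified this way is half of the evidence required.

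**Working it through.** **1. Which patients MLF adds beyond CR and CRi.** Take six yes/no items: circulating blasts, neutrophils ≥1.0, platelets ≥100, Auer rods, extramedullary leukemia, marrow ≤5%. They give 2⁶ = 64 combinations.

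- MLF holds in the 32 with marrow ≤5%. These are 8 patterns of the three disease signs × 4 patterns of counts.
- With all three signs absent, the 4 count patterns are one CR (both counts recovered) and three CRi (either or both low). None is left over.
- The other 7 × 4 = 28 combinations are MLF only. Each has circulating blasts, Auer rods or extramedullary leukemia.
- If 9.1.4 carried the same three exclusions, MLF would add 0 combinations beyond CR and CRi.

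These are counts of combinations, not of patients. They assume that every item is assessed and that blasts and myeloblasts mean the same.

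**2. Overlap with HI blast response, if read on marrow.** For a baseline marrow of b% and a later value of 5%, the reduction is 1 − 5/b. At b = 20 it is 75% and at b = 10 it is 50%, so any fall from 10% or more to 5% or less already counts as HI. At b = 9, 8 and 6 it is 44%, 38% and 17%, and at b = 5 it is 0%. Below 10% a patient may be MLF without being HI.

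**3. The plan's own design figures.** With response rate p:

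- Early termination = (1 − p)¹⁴. At 1% this is 86.9% (stated 87%).
- Success = 1 − (1 − p)¹⁴ − 14p(1 − p)²⁸. The last term is exactly one response in stage 1 and none in stage 2. At 1% this is 0.1313 − 0.1057 = 2.6% (stated 3%). At 20% it is 95.1% (stated 94.8%).

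The design is reproduced closely enough to use.

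**4. Illustration of the effect.** The documents give no frequency of MLF-only patients. Assume that a share q of patients counts through MLF alone, without drug benefit, on top of a true 1% rate.

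(a) MLF counts at the 14-patient look, as 9.1.6 implies. Put p = 0.01 + q in the formula above.

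(b) The CR+PR+HI list governs stage 1, so the look needs at least one response from the 1% (assumed here all to be of the listed types), while MLF counts in the final total: success = 1 − 0.99¹⁴ − 14 × 0.01 × (0.99 − q)²⁸.

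| q (assumed) | (a) MLF counts at the look | (b) CR+PR+HI list at the look |
|---|---|---|
| 0 | 2.6% | 2.6% |
| 1 point | 0.2464 − 0.1590 = 8.7% | 0.1313 − 0.0795 = 5.2% |
| 2 points | 0.3472 − 0.1790 = 16.8% | 0.1313 − 0.0597 = 7.2% |
| 4 points | 0.5123 − 0.1665 = 34.6% | 0.1313 − 0.0333 = 9.8% |

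Under (b), success cannot exceed 1 − 0.99¹⁴ = 13.1%, whatever q is.

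**The case against.** The strongest reply is that the ORR is deliberately broad. PR keeps marrow blasts above 5% and HI accepts a blast reduction or a count improvement, so residual disease counts as response with or without MLF. If HI blast response is read on marrow, most patients whose marrow clears from a substantial baseline are in the ORR already, and changing MLF would not remove them. This stands, and it limits the separate effect mainly to low-baseline patients. It does not reach the patient who enters at 5% or less: no reduction has occurred, so the blast line of HI does not apply. Nor is the overlap assured while the compartment is unstated.

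The claim that MLF-only patients must have one of the three signs also has limits. MLF says myeloblasts where CR and CRi say blasts. CR and CRi name aspirate and biopsy, while 8.2.5 schedules aspiration only, and the differential may be omitted at a low WBC. A patient could therefore be MLF because a CR/CRi item was never assessed. That is a further looseness in the definition, not a reason to keep it.

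Section 9.1 introduces its criteria as a brief summary of modified published criteria, and its opening sentence can be read as making MLF something that accompanies CR, CRi or PR. Whether the published source adds conditions cannot be checked here. Any that were intended need to stand in 9.1.4, since investigators assess response (11.2).

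**Conclusion.** The definition is defective as written: a component of the primary endpoint lacks both a baseline condition and the exclusions that its neighbours carry. The logic is exact for fully assessed patients with blasts read as myeloblasts. The size is uncertain. The percentages in the illustration rest on assumed frequencies and on which responder list governs the 14-patient look, a point on which 9.1.6 and section 11 disagree.

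Four stronger readings are not supported:

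- A reader might infer that MLF is what lets persistent leukemia count as response. PR and HI do so too.
- A reader might take 34.6% as the trial's false-positive rate. It is the top of an assumed range under one reading of the interim rule.
- A reader might treat every MLF-only patient as spurious. A fall from 30% to 4% marrow blasts with some circulating blasts left is a real change; only the patient at 5% or less on entry is clearly a response without change.
- A reader might say that the 1% null was set for a narrower endpoint. Section 11 states the null for the ORR and does not say which response definition lies behind the historical rate.

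**What to change.** Make one of two edits:

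- remove MLF from the ORR list in 9.1.6, which is the simpler course because MLF adds nothing beyond CR and CRi once the exclusions apply; or
- in 9.1.4, require marrow blasts above 5% at baseline together with absence of circulating blasts, Auer rods and extramedullary leukemia.

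With either, use the term blasts consistently across 9.1, state the compartment for HI blast response, and make the interim responder list in section 11 match 9.1.6.

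The cost is a few lines of text and possibly a slightly lower observed ORR. The second option asks for no item that CR and CRi do not already require. However, section 8 schedules no biopsy and no dedicated extramedullary assessment during treatment, so it should not be assumed that every item will be on record. The edit does not change how PR and HI treat residual disease.

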4.1 Inclusion Criteria

4.1.1 Patients with AML who have either been refractory to prior therapy or have relapsed after prior therapy. Patients with MDS or CMML who received therapy with a hypomethylating agent and progress to AML are eligible if they have received any therapy for MDS and failed (i.e., lack or loss of response) regardless of whether they have received therapy for AML or not. The WHO classification will be used for AML.

- 4.1.2** Age \geq 18 years
- 4.1.3** ECOG Performance Status \leq 2
- 4.1.4** Adequate liver (total bilirubin \leq 2x ULN, ALT \leq 2.5x ULN) and renal (creatinine \leq 2x ULN) function.
- 4.1.5** Patients must provide written informed consent.
- 4.1.6** Patients must have been off chemotherapy for 2 weeks prior to entering this study, unless there is evidence of rapidly progressive disease, and must have recovered from the clinically significant toxic effects of that therapy to at least grade 1. Use of hydroxyurea for patients with rapidly proliferative disease is allowed before the start of study therapy and for the first four weeks on therapy.
- 4.1.7** Patients – both males and females – with reproductive potential (ie, menopausal for less than 1 year and not surgically sterilized) must practice effective contraceptive measures throughout the study. Women of childbearing potential must provide a negative pregnancy test (serum or urine) within 14 days prior to initiation of study.

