11.0 STATISTICAL CONSIDERATIONS¹⁷

This is an open-label, to assess the efficacy and safety of erlotinib in patients with AML. The primary efficacy endpoint is overall response as defined in section 9.3.

The historical experience in this patient population is that response with standard therapy, when available, is less than 1%. In many instances (eg, patients with myelodysplastic syndrome failing hypomethylating agents), no standard therapy is even available. Thus, an overall response rate of 20% will be considered significant. For the purpose of this analysis, a response will be considered if occurring after 3 months of therapy (or earlier).

The Simon's optimal two-stage design will be used to implement the study. A total of 29 patients will be enrolled to this study. These sample sizes are based on Simon's optimal 2-stage designs of alpha=0.05 with power of 95% (beta=0.05) to test the null hypothesis that the ORR will be $\leq 1\%$ versus the alternative hypothesis that ORR will be ≥ 20 . At the first stage, 14 patients will be enrolled. If no response is observed among the 14 patients, the trial will be terminated early for futility. If one or more patients have response, 15 more patients will be enrolled at the 2nd stage. If at least 2 responses achieved after the completion of the 2nd stage, the study will conclude that the treatment improves the response rate from 1% to 20%. The probability of early termination under the null hypothesis is 87%. The probability of seeing at least 2 responses under the null (ORR = 1%) is 3% while the probability of seeing at least 2 with an event rate of 20% is 94.8%.

Further enrollment will continue during the interim analysis unless no responders (CR+PR+HI) have been reported by the time of enrollment of the 14th subject being analyzed. In this event, enrollment will be suspended and these 14 subjects will be followed to further assess their responses. During this follow-up period, as soon as one response is observed, enrollment will resume. If no response is observed after the 14 subjects have been fully assessed, the trial will be terminated for futility.

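### Hematologic improvement counts as a primary response with no condition on blasts, so a patient with worsening leukemia can be scored as a responder under a decision rule that needs only two

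*Combined protocol and SAP*

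**What the plan says.** Section 9.1.5 defines four HI categories: erythroid (E), platelet (P), neutrophil (N) and blast (B). Each is a threshold on change from pretreatment. N requires a pretreatment ANC below 1.0 x 10^9/L, then "At least 100% increase and an absolute increase" of more than 0.5 x 10^9/L. B requires a fall of at least half in blast percentage, without saying whether marrow or blood is meant. No category sets a condition on blasts elsewhere or on progression.

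Partial remission (section 9.1.3) requires at least a 50% fall in marrow blasts, plus "All CR criteria if abnormal before treatment except" the marrow item. Read literally, a CR item that was normal at entry does not have to stay normal.

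Section 9.1.6 then states: "An adequate response, included in the overall response rate (ORR) for this trial will include all of the following obtained within the first 3 months". HI is on that list, and section 11 names HI among the responses that count at the stage 1 look. Sections 11 and 11.2 refer to a section 9.3 for the definition, but the text has only 9.1. Section 3.0 mentions clinically significant progression as a reason to end treatment; it is not defined there or tied to response scoring.

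The decision rule is in section 11: "At the first stage, 14 patients will be enrolled", the trial stops if none of them responds, and it succeeds "If at least 2 responses achieved after the completion of the 2nd stage" of 29 patients.

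**The concern.** A responder should not be someone whose leukemia is getting worse, yet the written rules let this happen. Eligibility foresees fast-growing disease (section 4.1.6: "Use of hydroxyurea for patients with rapidly proliferative disease is allowed before the start of study therapy") and admits AML arising from CMML. With a 1% null and a success threshold of two responses, a few such scores could keep an inactive drug past the futility stop or make the trial positive.

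**Working it through.** **1. Do the rules score a worsening patient?** Two constructed examples.

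- *Example 1.* Pretreatment: WBC 3.0, neutrophils 20%, marrow blasts 35%. Day 21: WBC 30, neutrophils 5%, circulating blasts 85%. Day 28: marrow blasts 70%. ANC goes from 3.0 x 0.20 = 0.6 to 30 x 0.05 = 1.5. That is +0.9 (more than 0.5) and 0.9/0.6 = +150% (at least 100%), from a baseline below 1.0. All N conditions are met, so 9.1.6 counts the patient. Blasts are not being miscounted as neutrophils: the ANC rises because the WBC grows tenfold while the neutrophil share falls fourfold.
- *Example 2.* Pretreatment: marrow blasts 40%, no circulating blasts, platelets 120. Day 28: marrow blasts 18%, circulating blasts 10%, platelets 50. The marrow fall is (40 - 18)/40 = 55%. If B refers to marrow, this is a B response. It is also literally a PR, because circulating blasts and platelets were normal at entry and so are not tested.

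**2. Reproduce the design.** Inputs from section 11: 14 then 15 patients; stop at 0 of 14; success at 2 or more of 29; null 1%, alternative 20%; "Simon's optimal 2-stage designs of alpha=0.05 with power of 95% (beta=0.05").

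Early stop = (1 - p)^14.
Success = P(X1 = 1) x [1 - (1 - p)^15] + P(X1 >= 2), with X1 ~ Bin(14, p).

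- Early stop at p = 1%: 0.99^14 = 86.9% (stated 87%).
- Success at p = 1%: 0.1229 x 0.1399 + 0.0084 = 2.6% (stated 3%).
- Success at p = 20%: 0.1539 x 0.9648 + 0.8021 = 95.1% (stated 94.8%).

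The plan's figures are reproduced, allowing for rounding and a 0.3-point difference in power.

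**3. Sensitivity to false responses.** If a share f of true non-responders is scored as responding, the apparent null ORR is p = 0.01 + 0.99f.

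| Apparent null ORR | Calculation | Type I error | Early stop |
|---|---|---|---|
| 1% | as above | 2.6% | 86.9% |
| 1.45% | 0.1679 x 0.1968 + 0.0170 | 5.0% | 81.5% |
| 2% | 0.2153 x 0.2614 + 0.0310 | 8.7% | 75.4% |
| 3% | 0.2827 x 0.3667 + 0.0645 | 16.8% | 65.3% |

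The 5% level is passed at f of about 0.45%. One false responder in stage 1 defeats the futility stop outright; success then needs at least one more response among the other 28, which at 1% has probability 1 - 0.99^28 = 24.5%.

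**4. How large could f be?** The documents give no input, so everything here is assumed. In patients with proliferating disease and no drug effect: baseline ANC lognormal (median 0.4 to 0.6, log SD 0.7), and a WBC multiple and a neutrophil-share multiple each with log SD 0.5. The simulated false-N rate q enters as p = 0.01 + 0.99 x (share proliferating) x q.

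| WBC multiple x neutrophil-share multiple (median ANC change) | q | False success, 20% proliferating |
|---|---|---|
| 3 x 0.15 (0.45-fold) | about 1% | about 3.5% |
| 5 x 0.10 (0.5-fold) | about 1.3% | about 4% |
| 5 x 0.15 (0.75-fold) | about 4.6% | about 8% |
| 5 x 0.25 (1.25-fold) | about 15% | about 26% |
| 5 x 0.40 (2-fold) | about 33% | about 55% |

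If only 5% of patients proliferate, the 3 x 0.15 row gives p = 0.01 + 0.99 x 0.05 x 0.009 = 1.04% and false success of about 2.8%; the 5 x 0.15 row gives about 3.8%.

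**The case against.** The strongest objection is about mechanism. Section 2.0 describes AML as blocking normal marrow production and causing neutropenia, anemia and thrombocytopenia, so worsening disease should usually lower the counts that E, P and N need to rise. The criterion is on ANC, and weekly differentials separate blasts from neutrophils. Example 1 needs neutrophils to rise 2.5-fold while marrow blasts double. The simulation also ignores the hydroxyurea and leukapheresis allowed in cycle 1, and its top row assumes that the median progressing patient doubles the ANC. All of this stands as an argument about frequency. It does not supply the missing condition.

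Investigators assess response (section 11.2) and might not call such a patient a responder. But no written rule tells them to refuse, and criteria described as modified and given briefly cannot be presumed to carry an unstated exclusion.

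Three stronger readings are tempting and are not supported.

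- A reader might infer that new circulating blasts make a patient a responder. They do not: an HI or PR threshold must also be met.
- A reader might infer that PR is wide open to progression. It still requires the 50% marrow fall and clearance of circulating blasts present at entry. The gap is limited to CR items normal at entry. If B means marrow blasts, every PR is also a B response, so rewording 9.1.3 alone would not change the ORR.
- A reader might infer a false-positive rate above 50%. That rests wholly on the least favorable assumed inputs.

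**Conclusion.** The point holds, mainly for HI. Followed exactly, sections 9.1.5 and 9.1.6 can count a patient with worsening leukemia in the primary ORR and at the stage 1 look. What is firm is the fragility of the rule: about 0.45 percentage points of false response is enough to exceed the design's 5% alpha, and one false response in the first 14 removes the futility stop. That follows from section 11 alone. What is not known is the frequency. Under the assumed kinetics, with 5% to 20% of patients proliferating, false success lies between about 3%, which is negligible inflation over 2.6%, and about 55%. The case for a change is that the rule is wrong as written and cheap to correct, and does not depend on any one of these values.

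**What to change.** Add to sections 9.1.5 and 9.1.6:

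> *An HI response in any category (E, P, N or B), and a PR, counts toward the ORR, including the stage 1 count, only if the circulating blast percentage on the same CBC is not above pretreatment (none, if none were present before treatment) and the blast percentage on the most recent marrow is not above pretreatment.*

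The condition should be stated in these measured terms and not made to depend on progression having been declared, since the protocol does not define progression for response scoring. B must be included, or example 2 would still count. Example 1 is removed by its day 21 CBC: with 20% neutrophils at entry, pretreatment circulating blasts were at most 80%, against 85% on that CBC.

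In section 9.1.3, clarify that the CR items other than marrow blasts must be met at the response assessment whether or not they were abnormal before treatment. This corrects the PR category; the sentence above is what protects the ORR.

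The cost is a few lines of protocol text. The weekly CBC with differential and the day 28 and later marrows are already scheduled in section 8.2. No patients or visits are added, and treatment rules are untouched. The downside is that an occasional genuine lineage improvement accompanied by a minor blast fluctuation would not count.

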8.1.7 Chest x-ray

8.2 Evaluation During Treatment: All tests are ± 5 days unless otherwise specified.

8.2.1 Physical exam after 28 days of therapy (± 7 days), then every 2-3 months.

8.2.2 Assessment of adverse events.

8.2.3 CBC, platelet count, differential once weekly for the first 3 months, then every 2-4 weeks (differential can be omitted if WBC is $\leq 0.5 \times 10^9/L$) until 6 months of therapy, then every 6-8 weeks.

8.2.4 Creatinine, total bilirubin, ALT weekly for the first 3 months, then every 2-4 weeks until 6 months of therapy, then every 6-8 weeks.

8.2.5 Bone marrow aspiration on day 28 (± 7 days), then every 2-3 months for 1 year; then as clinically indicated. Bone marrow aspirations to be performed at MDACC.

8.2.6 Correlative studies (Appendix A). Every effort will be made to collect all samples at all time points for all patients; however, missing collection in one or more of these time points in occasional patients will not be considered a protocol deviation/violation.

8.2.7 For patients that remain on study with no significant toxicity for more than 12 months, subsequent evaluations during study may be modified after discussion with the principal investigator. These include a decrease in frequency of correlative studies and other laboratory tests to once every one to three cycles.

8.2.8 For patients receiving concomitant warfarin, PT at least every 4 weeks for the first 6 months or more frequent if clinically indicated; after the first 6 months, PT as clinically indicated.

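### Blast response (B) names no compartment and has no baseline floor, yet alone makes a primary responder, so counting noise in low circulating blasts can score as a response

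*Combined protocol and SAP*

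**What the plan says.** Section 9.1.5 lists four lines of hematologic improvement (HI).

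- **Erythroid, platelet and neutrophil:** each applies only below a pretreatment limit (the erythroid line opens with "pretreatment Hgb" under 11 g/dL; platelets under 100; ANC under 1.0). Each also asks for an absolute rise or, for platelets starting below 20, for crossing 20 and at least doubling.
- **Blast:** the whole rule is "at least 50% reduction in blast percentage".

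No minimum number of lines is required. The text says only that "Hematologic response must be described by the number of positively affected cell lines". No confirmation or duration is asked for.

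Section 9.1.6 counts as overall response any of the following "obtained within the first 3 months of therapy: CR, CRi, PR, MLF, HI". Section 11.0 counts HI at the interim too: enrollment continues "unless no responders (CR+PR+HI) have been reported". Under 11.0, no response in 14 stops the trial for futility, and 2 responses in 29 declare success against a null ORR of 1%.

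Partial remission (9.1.3) does name its compartment: at least a 50% "reduction in bone marrow blast but still" above 5%, together with "All CR criteria if abnormal before treatment except" the marrow blast item. Section 8.2.3 schedules "CBC, platelet count, differential once weekly for the first 3 months". Section 8.2.5 schedules marrow aspirates at day 28 and then every 2-3 months.

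**The concern.** The rule as written can be met by something that is not a response. With blood as the compartment, going from 2% to 1% is a reduction of (2 - 1)/2 = 50%, which qualifies whatever the marrow shows. A differential counts a limited number of cells, so a patient whose true blast percentage never changes can produce that fall by chance, and weekly sampling over the 3-month response window gives many opportunities.

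The decision rule has little room for this. One response removes the stage 1 futility stop, and two declare the drug active. Section 11.0 justifies the 1% null as the response rate on standard therapy. Nothing there shows that the figure covers an unconfirmed halving of a blast percentage.

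**Working it through.** **1. The plan's own design.** With 14 then 15 patients, going on with at least 1 response and succeeding with at least 2:

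P(pass) = P(X1 >= 2) + P(X1 = 1) x P(X2 >= 1).

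- At 1%: 0.0084 + 0.1229 x (1 - 0.8601) = 0.0256. Early stopping: 0.99^14 = 0.869.
- At 20%: 0.8021 + 0.1539 x (1 - 0.0352) = 0.9506.

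The plan states 3%, 87% and 94.8%. The design arithmetic therefore reproduces to within rounding (2.6%, 86.9%, 95.1%). The question is whether 1% is the right null rate for an endpoint that includes B.

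**2. Chance of a spurious B on a blood reading.** Assumptions, none in the documents: true blast percentage p constant; m cells counted, so each count is Binomial(m, p); baseline count b at least 1; any one reading at or below b/2 counts. The weekly schedule is from 8.2.3; 13 readings is about 3 months.

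P = sum over b >= 1 of P(b | b >= 1) x [1 - (1 - P(Y <= b/2))^k], for k readings.

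Single-term check: with b = 2 in 100 cells and p = 2%, P(Y <= 1) = 0.98^100 + 100 x 0.02 x 0.98^99 = 0.133 + 0.271 = 0.40. Averaging over all baseline counts gives 37%, the first entry below.

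| Cells, readings | 2% | 3% | 5% | 10% |
|---|---|---|---|---|
| 100, one | 37% | 28% | 18% | 7% |
| 100, four | 76% | 64% | 47% | 23% |
| 100, thirteen | 95% | 89% | 76% | 48% |
| 200, thirteen | 83% | 71% | 49% | 16% |

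The effect fades at higher blast percentages: 100 cells and 13 readings give 12% at 20% blasts and 2% at 30%.

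**3. Consequence for the two-stage rule.** Suppose k of the 29 patients respond spuriously with probability q and all others respond at 1%. The k patients fall at random between the stages, with weight C(14,j) x C(15,k-j) / C(29,k) for j of them in stage 1. For k = 1 and q = 0.5, P(pass) is 13.4% if the patient is in stage 1 and 7.8% if in stage 2: (14/29) x 13.4% + (15/29) x 7.8% = 10.5%.

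| Patients k | q = 7% | q = 18% | q = 50% | q = 90% |
|---|---|---|---|---|
| 1 | 3.5% | 5.3% | 10.5% | 17.0% |
| 2 | 4.7% | 9.3% | 29% | 66% |
| 3 | 5.9% | 14% | 47% | 84% |

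The comparator is 2.6%.

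**4. Marrow reading.** The formula in step 2, with m = 200, p = 20% and one reading, gives 0.06%, or about 0.1%. At p = 10% it gives 1.7%. A halving from a baseline of 10% or less ends at 5% or less, which already counts as morphologic leukemia-free state under 9.1.4, so B adds responders only above that range.

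**The case against.** **Size.** The strongest objection is that the large figures stack assumptions. They need the blood reading, a small differential, a constant blast percentage for 13 weeks in relapsed or refractory AML with the patient still on treatment, acceptance of one unconfirmed reading, and several patients with few circulating blasts. Only the weekly sampling is in the documents. This stands. A reader might infer that the false-positive rate is 47-84%, but that is the upper corner of the range (three patients at 50-90%). With one patient at 7% it is 3.5%.

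**Which compartment.** Section 9.1 gives its criteria in brief, as modified from a published set, and B may have been meant as marrow. In that case the noise nearly disappears. This stands too: the documents show an open definition, not a null rate proved wrong. But nothing in them supplies the compartment or a floor.

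**Whether HI alone counts.** The opening of 9.1 can be read as limiting responders to CR, CRi and PR. Section 9.1.6 is the explicit ORR definition, however, and 11.0 counts HI at the interim, so this does not remove the problem.

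**Partial remission.** A reader might infer that a marrow-based B makes the PR conditions an error. It is true that every PR would then also be B, as would a marrow halving that fails PR on circulating blasts, neutrophils or platelets. But nesting is common in a composite endpoint. Morphologic leukemia-free state, which asks only for marrow blasts of 5% or less, does the same to the count conditions of CR and CRi. PR keeps its use as a response category. Counting marrow halvings as activity is a sponsor choice that should be stated openly.

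**Conclusion.** The concern holds as a defect of definition in a component of the primary endpoint. As written, B lets a 2% to 1% change on a single blood differential make a primary responder, and a stable patient can produce that by chance.

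The size depends on inputs the documents do not give. Over 1 to 3 low-blast patients and a per-patient chance of 7-90%, an inactive drug passes with probability of about 4-84%, against 2.6%. One patient at 50-90% is enough for about 11-17%, above the stated alpha of 0.05. One patient at 7% is not (3.5%).

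The documents do not support the stronger conclusions that the 1% null has been shown to be invalid or that B-only patients must be left out of the response counts. The second would remove a component the sponsor chose to include, and the 20% alternative was set for an ORR that contains it.

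**What to change.** In 9.1.5, define B as at least a 50% reduction in the bone marrow aspirate blast percentage, in patients with pretreatment marrow blasts above 5% (the cut-off already used in 9.1). State that blood differentials alone do not qualify. State also whether a marrow halving that fails the other PR conditions is intended to count. Report the number of B-only responders in a separate row next to the ORR.

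The cost is wording only, since the marrows in 8.2.5 are already scheduled. The downside is that the reported ORR may be lower.

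Leaving B-only patients out of the stage 1 (at least 1 in 14) and final (at least 2 in 29) counts is optional. It could lower power and raise the chance of a futility stop, so the design's power would have to be re-examined first.
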